7.8. Anti-Drug Antibody

The number, titer and associated percentage of patients who are ADA positive at baseline and also, at any post-baseline visit will be summarized. A listing of AEs for patients with ADA positivity will be provided.

A listing of all ADA data will be provided.

7.9. COVID-19 Pandemic Impact Analyses

Additional data were collected to characterize the impact of the COVID-19 pandemic on general study conduct, disposition, and quality of life, and subsequently, additional analyses and summaries will be provided in acknowledgement of multiple regulatory guidances (FDA Guidance on Conduct of Clinical Trials of Medical Products during COVID-19 Pandemic: Guidance for Industry, Investigators, and Institutional Review Boards, US Food and Drug Administration, 2020; Guidance on the Management of Clinical Trials during the COVID-19 (Coronavirus) Pandemic, European Medicines Agency, 2020; Points to consider on implications of Coronavirus disease (COVID-19) on methodological aspects of ongoing clinical trials, European Medicines Agency, 2020; Statistical Considerations for Clinical Trials During the COVID-19 Public Health Emergency, US Food and Drug Administration, 2020).

7.9.1 General impact

Patients who discontinue treatment or stop study participation due to COVID-19 pandemic will be included in patient disposition summaries. Impact on study participation due to COVID-19 pandemic, including visit completion, visit location changes, and study drug dosing and location changes, will be summarized overall on the patient level, and overall and by visit on the event level.

7.9.2 Impact on Efficacy

COVID-19 pandemic impacted efficacy analyses are not carried out for the primary analysis since efficacy assessments (e.g., blood and urine samples for PD, renal ultrasound data) missed due to COVID-19 pandemic are minimal.

However, the final analyses will include COVID-19 pandemic impacted efficacy analyses. The analyses will evaluate the impact of changes in the visit windows for the efficacy assessments made in the protocol amendment 2 (dated 04 May 2020) due to COVID-19 pandemic. Missing efficacy data due to the COVID-19 pandemic will be summarized.

7.9.3 Impact on Adverse Events

Events will be considered during the COVID-19 pandemic if the event occurs on or after first confirmed case of COVID-19 based on the country where the study site is located, described in Appendix 10.7.

An overall summary of AEs mapping to a COVID-19 custom query will include the number and percentage of patients, as well as events and event rates, with any AE, any AE related to study drug, any severe AE, any severe AE related to study drug, any SAE, any SAE related to study drug, any AE leading to treatment discontinuation, any study drug related AE leading to treatment discontinuation, any AE leading to study withdrawal, any study drug related AE leading to study withdrawal, and any deaths. AEs mapping to the COVID-19 custom query will be summarized by high level term and preferred term. Due to the evolving nature of COVID-19-related MedDRA terminology, the COVID-19 custom query will be based on the latest information available at the specified analysis timepoints.

An overall summary of AEs by COVID-19 pandemic phase (i.e., pre-, during, and post) will include the number and percentage of patients, as well as events and event rates, with any AE and any SAE.

7.9.4 Other Impacts

Treatment duration will also be summarized by pandemic phase. Protocol deviation due to COVID-19 pandemic will be summarized and will be indicated in the listing of protocol deviation. Adverse event, study drug exposure, and efficacy listings will include identification of assessments occurring during the pandemic. For patients reporting an AE mapped to the COVID-19 custom query, AEs and prior and concomitant medications will also be presented in separate data listings. Additionally, patient profiles will be provided.

8. CHANGES TO PLANNED ANALYSES

Summary of Changes from SAP V2.0	Rationale
Section 7.9 and Appendix 10.7 are added	To add the analysis plan for COVID-19 pandemic impact
Remove the imputation for analyses of 24-Hour Urinary Oxalate Excretion in Section 7.1.2	24-hour urine data are only available from few patients. Imputation planned initially will not lead meaningful results and thus will not be carried out
The definition of PK Analysis Set is changed in Section 4.1	PK Analysis Set is defined using all patients who received “one full” dose rather than “any amount” dose of lumasiran to account patients with adequate study drug exposure
Add additional analysis for changes in plasma oxalate for patients whose baseline POx \geq 1.5xLLOQ in Section 7.3	The LLOQ of the plasma oxalate assay is 5.55 μ mol/L. Due to the inability of quantify oxalate level below LLOQ by the assay, additional analysis is added so that meaningful reduction can be quantified
Change clinical laboratory data source and detailed analysis plan in Section 7.7.3	To align with the change in Protocol Amendment 2.0, the data handling for both central and local clinical laboratory data is added
Various editorial changes	To improve clarity

10. APPENDICES

10.1. Urinary Oxalate calculation

10.1.1. Spot Urinary Oxalate:Creatinine Ratio

Spot urinary UOx:Cr ratio is calculated using single urine void with spot urinary oxalate normalized by creatinine concentration to account for differences in urinary dilution. The unit of spot urinary UOx:Cr ratio is mmol/mmol.

10.1.2. 24-Hour Urinary Oxalate Corrected for BSA

24-hour urinary oxalate (mmol/24hrs/1.73m²) corrected for BSA at each visit per patient is calculated as follows:

Urinary oxalate concentration (umol/L)/1000 (umol/mmol)*24hr urinary volume (mL)/1000 (mL/L)*24 hours/actual collection hours*1.73/(BSA)

where BSA is calculated using the Mosteller formula:

BSA=square root (mean height (cm)*weight (kg)/3600) at the visit.

Only valid 24-hour urinary oxalate values will be considered for analysis. (note: valid is defined as: creatinine \geq 5 mg/kg, duration of collection 18 to 26 hours, no missing voids and the sample was not collected within 14 days after the most recent dialysis session, if applicable).

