### **6.2. Efficacy Assessments**

24-hour urine collections are the preferred method of evaluating urinary oxalate levels. Since not all patients will be able to provide 24-hour urine samples, single-void urine samples (in triplicate) will be collected throughout the study in all patients. [Table 9](#) shows the 24-hour urine collection procedure by study visit.

In children who are able to comply with 24-hour urine collection procedures, urinary oxalate excretion will be determined from 24-hour urine sample collections to be completed at the time points specified in the Schedules of Assessment (see [Table 1](#), [Table 2](#), [Table 3](#), and [Table 4](#)). Urinary oxalate concentrations will be analyzed centrally using a validated assay. Non-catheterized 24-hour urine collections must meet pre-specified validity criteria (see [Section 6.2.1.1](#)). The duration of collection and volume of urine in the collection will be recorded in the eCRF.

For patients who are able to comply with the 24-hour urine collection procedure, three 24-hour urine collections will be scheduled during screening to establish baseline urinary oxalate excretion. For Month 6, three 24-hour urine collections will be scheduled within 14 days prior to the Month 6 dose to evaluate changes in oxalate concentrations over the first 6-month interval. A single 24-hour collection will be scheduled at Month 12 and then every 6 months thereafter.

Patients able to comply with 24-hour urine collections will either bring a 24-hour urine collection to the clinic, courier samples to the laboratory, or have their 24-hour urine collected during an inpatient stay at the time of the study visit.

For patients who are unable to comply with 24-hour urine collections, a single catheterized 24-hour collection will be obtained, when allowed, at both baseline and Month 6. Catheterized collections may be performed at the discretion of the Investigator and with the consent of the legal guardian. Catheterized collections will be considered complete if there is no documented urine loss during the collection.

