#### **6.2.1.1. Validity Criteria for Non-catheterized 24-hour Urine Collections**

A urine collection will be considered valid if each of the following criteria are met:

- The collection is between 18-26 hours in duration between the initial discarded void and the last void or attempt to void.
- No voids are missed between the start and end time of the collection.
- The 24-hour creatinine content is at least 5 mg/kg as assessed by the study central lab.

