7.1.2. Analyses of 24-Hour Urinary Oxalate Excretion

24-hour urinary oxalate analysis will be conducted to assess the robustness of the primary outcome. Only valid 24-hour urinary oxalate values (see Section 6.2.1.1 of the protocol) will be considered for analysis for patients in Efficacy Analysis Set. The correlation between spot urine and 24-hour collection urine values maybe investigated. The analyses for 24-hour urinary oxalate corrected for BSA and 24-hour urinary UOx:Cr ratio will be carried out with data as observed. Percent change from baseline of 24h urinary oxalate corrected for BSA and 24h UOx:Cr ratio through Month 6 will be summarized.

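### Read literally, the SAP's definition of a valid 24-hour urine can exclude catheterized collections that the protocol accepts as complete

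*SAP*

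**What the plan says.** **Protocol.** Section 6.2 provides two routes to a 24-hour urine. Children who can comply give voided collections, and these must meet the criteria in Section 6.2.1.1, which is headed "Validity Criteria for Non-catheterized 24-hour Urine Collections". The criteria are a duration of 18 to 26 hours, no missed voids, and a creatinine content of at least 5 mg/kg. Children who cannot comply may have one catheterized collection at baseline and one at Month 6, when allowed. For these the protocol gives a single test: "Catheterized collections will be considered complete if there is no documented urine loss during the collection".

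**SAP.** Section 7.1.2 uses the 24-hour data to check the robustness of the primary outcome, and says: "Only valid 24-hour urinary oxalate values (see Section 6.2.1.1 of the protocol) will be considered for analysis for patients in Efficacy Analysis Set". Section 10.1.2 repeats the restriction ("Only valid 24-hour urinary oxalate values will be considered for analysis") and then gives its own definition of valid: the same 5 mg/kg creatinine minimum, together with "duration of collection 18 to 26 hours, no missing voids" and, where applicable, a condition that rules out samples taken in the 14 days following dialysis. Neither section mentions catheterized collections. SAP Section 8 explains why imputation was removed: "24-hour urine data are only available from few patients".

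**The concern.** The protocol has two acceptance tests, one for each collection method. The SAP carries over one of them and words it as if it covered all 24-hour samples. A programmer working from Section 10.1.2 would remove a catheterized sample that lasted less than 18 or more than 26 hours, or that fell below the creatinine minimum, even if no urine was lost.

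At stake is the 24-hour check on the spot-urine result. SAP Section 7.1 says that the existing correlation between spot and 24-hour values comes from patients older than 6 years, whereas this trial enrols children under 6. The 24-hour pairs collected here are therefore the within-trial evidence on that link at the target ages. They are few, they are analysed as observed, and a catheterized child has no second sample at either visit.

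**Working it through.** The documents give no figure on this point, so there is nothing to reproduce. The check is a comparison of texts, followed by an illustration of why lack of replication matters.

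**Step 1. The rules side by side**

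| Condition | Protocol, non-catheterized (6.2.1.1) | Protocol, catheterized (6.2) | SAP, all 24-hour values (10.1.2) |
|---|---|---|---|
| Duration 18 to 26 hours | yes | not stated | yes |
| No missed voids | yes | not stated | yes |
| Creatinine at least 5 mg/kg | yes | not stated | yes |
| No documented urine loss | not stated | yes | not stated |
| Not within 14 days after dialysis | not stated | not stated | yes |

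The SAP column holds all three non-catheterized conditions and omits the catheterized one. It also adds a dialysis condition that protocol Section 6.2.1.1 lacks, so Section 10.1.2 is more than an abbreviation of that section.

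**Step 2. Which criteria can exclude a complete catheterized sample.** A catheterized collection without urine loss largely meets the missed-void condition by design. That leaves duration and the creatinine minimum.

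**Step 3. Replication.** Protocol Table 9 plans three voided collections or one catheterized collection at Screening, and the same at Month 6. Suppose that each collection independently fails a criterion with probability q, and that one valid sample per visit is enough for a change from baseline. The chance that a child loses the baseline-to-Month-6 change is then:

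- one catheterized collection per visit: 1 − (1 − q)²
- three voided collections per visit: 1 − (1 − q³)²

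| q (assumed) | Catheterized | Voided |
|---|---|---|
| 5% | 1 − 0.95² = 9.8% | 1 − (1 − 0.000125)² = 0.02% |
| 10% | 1 − 0.90² = 19.0% | 1 − (1 − 0.001)² = 0.2% |
| 20% | 1 − 0.80² = 36.0% | 1 − (1 − 0.008)² = 1.6% |
| 30% | 1 − 0.70² = 51.0% | 1 − (1 − 0.027)² = 5.3% |

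The documents give no failure rate, so the values of q are assumptions. The table shows only that the same rule costs a catheterized child far more than a child with three voided samples. A lost baseline would also remove any later 24-hour change from baseline in that child.

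**Step 4. Duration.** The formula in SAP Section 10.1.2 multiplies by 24 divided by the actual hours. Within the window the factor runs from 24/26 = 0.92 to 24/18 = 1.33. A hypothetical 6-hour sample would be multiplied by 24/6 = 4. The scaling allows for modest departures from 24 hours but does not make duration irrelevant.

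**The case against.** The strongest reply is that SAP Section 7.1.2, the operative analysis text, defines validity by pointing to a protocol section whose heading covers non-catheterized collections only. On that view the note in Section 10.1.2 is shorthand for the same rule, and catheterized samples are exempt. SAP Section 1 promises that changes to the protocol's methods will be described in Section 8, and Section 8 lists none on this point. This has force. A reader might infer that the SAP deliberately overrides the protocol, and the documents do not support that; they show a literal rule that conflicts with the protocol. The reply does not settle the matter, because Section 10.1.2 stands alone as a definition and has no exemption. If the citation governs instead, the SAP has no rule at all for catheterized samples.

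Second, the protocol calls such samples complete, not valid, and does not say that they enter the analysis whatever their duration. That stands, and it is why the remedy should not simply abolish the duration check.

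Third, the consequence is limited. Catheterization is optional, at the investigator's discretion and with the guardian's consent. Excluded values would still appear in the listings. From Month 12 the 24-hour schedule is voided only. All of this stands.

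**Conclusion.** The mismatch is real and minor. Followed literally, SAP Section 10.1.2 can exclude catheterized collections that meet the protocol's only stated test for them, in a supportive analysis with few patients, no imputation and no replicate for those children.

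The size cannot be given. The documents state neither how many catheterized collections exist nor how many would fail on duration or creatinine, and the number affected may be zero. The percentages in the working rest on assumed, independent failure rates.

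Three stronger readings are not supported:

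- **A known share of the 24-hour pairs is lost.** The SAP says only that few patients have such data.
- **The loss falls mainly on the youngest children.** This is plausible, but the protocol ties catheterization to inability to comply and gives no age link.
- **The primary result is at risk.** The primary endpoint and membership of the Efficacy Analysis Set both depend on spot urine.

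**What to change.** In SAP Sections 7.1.2 and 10.1.2:

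1. Apply the creatinine and missed-void criteria to non-catheterized collections only.
2. Accept catheterized collections with no documented urine loss, in line with protocol Section 6.2.
3. State the duration condition for catheterized collections explicitly, or present the 24-hour results with and without catheterized samples outside 18 to 26 hours. Do not drop every duration check, because values are scaled by actual hours.
4. Report the 24-hour collections excluded, by collection method and reason.

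The cost is a clause in each of the two SAP sections and one small table or listing. No new data are needed, because the protocol already records collection duration and rests catheterized completeness on documented urine loss. The primary analysis does not change.

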10.2. Spot Urinary UOx:Cr Ratio Given Natural Growth

10.2.1. Natural decline of spot urinary UOx:Cr ratio in healthy pediatric population

Cross sectional studies, where the spot urinary UOx:Cr ratios were compared across broad age ranges (e.g., 1 - 6 months, 6 – 12 months, 1 – 2 years), showed that in young children over the age range of 0 to about 8 years, the urinary UOx:Cr ratio declines with increasing age. Data from healthy children ages 1 month to 17 years old (N=386) showed a decline in the 95th percentile of the spot urinary UOx:Cr ratio.[Matos 1999]. The decline in the UOx:Cr ratio appears to plateau after 7 years of age.[Matos 1999] A similar publication using data from 188 children from birth to 16 years old showed that the mean (and 5 – 95th percentiles) of the UOx:Cr ratio declined with increasing age, with no further decline observed in children ages 9 and above.[Leumann 1990]

[figure not shown]
On the other hand, longitudinal data based on 30 healthy infants where intensive random urine samples were collected starting from day 2 of birth with additional samples collected on weeks 2, 8, 16, 24 and 36 show that the mean UOx:Cr ratio stays stable over a period of 8 months (day 2 to week 36).[Morgenstern 1993] These findings are consistent with the results of another cross-sectional study where the mean (5 – 95th percentile) of UOx:Cr ratios stayed stable from birth up to 1 year of age.[Reusz 1995] Relative to other cross-sectional studies, Reusz compared UOx:Cr ratios using age categories with narrow age ranges.[Reusz 1995]

10.2.2. Effect of Age on Spot urinary UOx:Cr ratio in pediatric PH1 patients

There is limited longitudinal data of spot urinary UOx:Cr ratio in pediatric PH1 patients. Lieske reported spot urinary UOx:Cr ratio from 35 PH1 patients across ages from international registry of primary hyperoxaluria.[Lieske 2005] Of these patients, 15 children are under 7 years old, with 2 less than 2 years old.

To check whether similar decline is observed in PH1 patients as in selected studies involving unaffected children, single values of individual patient spot UOx:Cr (plotted in [Figure 1](#)) were read from Lieske's paper using Digitize (R package). Lieske's data are shown in [Figure 1](#) along with the reference curves for Lower limit of normal (LLN) and ULN identified by Matos' publication. All patients except for one patient under 1 year old had spot urinary UOx:Cr ratios above the Matos ULN.

Figure 1: Spot urinary UOx:Cr ratio (mmol/mmol) in children with PH1 based on [Lieske 2005] Data

10.3. Urinary Excretion Correlation Between Spot and 24-Hour Values

[figure not shown]
The correlation between percent reduction from baseline in spot urinary UOx:Cr ratio and 24-hour urinary oxalate excretion relative to baseline was evaluated based on ALN-GO1-001 data collected on August 18, 2018. Four patients were excluded due to a laboratory processing issue leading to potentially erroneous results in the UOx:Cr ratios from spot samples. A total of 156 paired samples from 16 patients are included in the analysis. The correlation between time-matched UOx:Cr ratios from spot urinary samples and oxalate excretion from 24-hour urinary collections was strong, with a Pearson correlation coefficient of 0.86 (95% CI: [0.82, 0.90]).

Table 2: Percent Reduction from Baseline over Time of Spot Urinary Oxalate: Creatinine Ratios Vs 24-Hour Urinary Oxalate Excretion in Study 001B

Study Day		24-hour Collections Urinary Oxalate Excretion	Spot Urinary Oxalate:Creatinine Ratio
	N	Mean % Reduction (SEM)	Mean % Reduction (SEM)
Day 29	14	49.8 (5.2)	51.9 (6.8)
Day 57	15	63.3 (4.2)	59.3 (5.7)
Day 85	13	63.2 (4.4)	60.9 (6.7)
Day 113	13	70.8 (4.1)	60.0 (6.0)
Day 141	13	70.9 (3.0)	63.9 (6.6)
Day 169	11	63.3 (5.0)	70.2 (4.0)

[figure not shown]
The observed mean percent reduction and standard error are similar in both urinary sample types (Table 2). The data also show sustained reduction over time in both urinary sample types.

Figure 2: Scatterplot of Spot Urinary Oxalate:Creatinine Ratios vs 24-hour Urinary Oxalate Excretion in Study 001B

[figure not shown]
Time-matched paired samples are plotted from 20 patients enrolled in Part B, ALN-GO1-001 demonstrating a linear relationship. Regression: spot ratio = $-0.004 + 0.083 \times$ 24-hour urinary oxalate; $R^2=0.774$.

Figure 3: Scatterplot of Percent Change from Baseline in Spot Urinary Oxalate: Creatinine Ratios vs 24-hour Urinary Oxalate Excretion in Study 001B

Time-matched paired samples are plotted from 16 patients enrolled in Part B, ALN-GO1-001 demonstrating a linear relationship. Regression: spot ratio = $-4.625 + 0.885 \times 24\text{-hour urinary oxalate}$; $R^2=0.656$.

Figure 4: Percent Coefficient of Variation Comparison of Spot Urinary Oxalate: Creatinine and 24-Hour Urinary Oxalate Excretion

For each patient, the percent coefficient of variation was calculated using $(\text{standard deviation} / \text{mean}) * 100\%$. A histogram of the results is presented for spot urinary (blue) and 24-hour urinary excretion (red). The fitted curves represent the normal distribution for each of the sample types.

Table 3: Observed Percent Coefficient of Variation from Spot Urinary Oxalate: Creatinine Ratios vs 24-Hour Urinary Oxalate Excretion

Urinary Sample	N	Mean	95% CL Mean	Std Dev	Min	Max
Spot Ox/Cr ratio CV (%)	20	55.5	[38.06, 72.96]	37.29	13.2	143.5
24hr oxalate CV (%)	20	52.6	[40.47, 64.75]	25.93	16.8	101.2
CV Difference (%)	20	2.9	[-7.07, 12.87]	4.76	-43.1	50.0

The population mean %CV is presented for both sample types. In addition, the mean of the differences between spot urinary samples and 24-hour collections is also presented.

Histograms depicting the coefficients of variation for spot urinary and 24-hour urinary samples are plotted, the mean and standard deviation for these coefficients of variation are similar (Figure 4 and Table 3). The correlation between the spot urinary UOx:Cr ratios and 24-hour urinary oxalate excretion coefficients of variation was strong, with a Pearson correlation coefficient of 0.83 [0.62, 0.93]. The difference between the coefficients of variation was 2.9% [-7.1%, 12.9%]. Therefore, the analysis of the data suggests that the correlation of variation for spot urinary samples is similar to that observed for 24-hour urinary samples. This supports the previous findings that the variations between the urinary sample types are minimal.

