If the fit of the autoregressive (1) covariance structure matrix fails to converge, the primary estimate will be calculated as the LS mean of the primary outcome variable average across scheduled visits of Month 3 to Month 6 (based on available measures), according to analysis of covariance (ANCOVA) model with covariate of baseline spot urinary UOx:Cr ratio value (mmol/mmol). This LS mean will be presented along with corresponding SEMs, 95% CI and p-value from the model.

Descriptive statistics will also be generated at each scheduled visit. Mean (+/- SEM) figures of percent reduction will be plotted as well as individual spaghetti plots and listings. A table of the mean maximum percent reduction during the 6-months will also be generated.

Missing data on 24-hour urinary oxalate corrected for BSA are expected in the pediatric patients to be enrolled in this study. Existing correlation analysis based on PH1 patients older than 6 years old of 24-hour urinary oxalate corrected for BSA and spot urinary UOx:Cr ratio is included in Section 10.3.

Primary Interim Analysis

A similar analysis will be performed for the primary interim efficacy analysis set, i.e., among the first 16 enrolled patients, those who received any amount of lumasiran and have at least one

valid spot urinary UOx:Cr ratio value at baseline and at least one valid spot urinary UOx:Cr ratio value from assessment(s) from Month 3 through Month 6.

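### Does the standard error printed as a standard deviation in SAP Section 10.3, Table 3, and the conclusion beside it, call for a change to the plan?

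*SAP*

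**What the plan says.** The primary outcome is the percent change from baseline in the spot oxalate:creatinine ratio, averaged over Months 3 to 6 (SAP Sections 3.1 and 7.1). Protocol Section 6.2 prefers 24-hour collection but accepts that not every child can provide it, so spot samples are taken from everyone. For the relation between the two measures, SAP Section 7.1 points to Section 10.3 and describes its source: "Existing correlation analysis based on PH1 patients older than 6 years old".

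Section 10.3 reports data from Study ALN-GO1-001:

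- Four patients were left out because of a laboratory problem with their spot ratios. The text then says "A total of 156 paired samples from 16 patients are included in the analysis" and gives r = 0.86 (95% CI 0.82 to 0.90).
- On Table 2 it says "The observed mean percent reduction and standard error are similar in both urinary sample types (Table 2").
- The Figure 2 note says "Time-matched paired samples are plotted from 20 patients enrolled in Part B", with R² 0.774. The Figure 3 note, on percent change, says "Time-matched paired samples are plotted from 16 patients enrolled in Part B", with R² 0.656.
- Table 3 gives, for 20 patients, the CV of each sample type and the CV difference. The text reports a correlation of 0.83 (0.62 to 0.93) between the two CVs and a mean difference of 2.9 points (-7.1 to 12.9), and concludes: "This supports the previous findings that the variations between the urinary sample types are minimal".

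**The concern.** In the CV-difference row, a standard deviation of 4.76 cannot be squared with the confidence limits or the range printed beside it. Taken at face value, it makes the two sample types look interchangeable patient by patient, which the rest of the row contradicts. The closing sentence then seems to rest on a misprint.

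Three further features of the appendix point the same way. Table 2's standard errors are called similar, although the spot value is the larger at five of six visits. The interval around r = 0.86 may treat 156 repeated samples from 16 patients as independent. The four patients excluded for suspect spot ratios reappear, unexplained, in Figure 2 and Table 3.

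If the choice of the spot ratio as primary outcome depended on these figures, the support for the endpoint would be overstated.

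**Working it through.** **1. What the Std Dev column holds.** Inputs are the three rows of Table 3, N = 20 each. With t(0.975, 19 df) = 2.093 and √20 = 4.472, SE = half-width / 2.093 and SD = SE × 4.472.

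| Row | Half-width of 95% limits | SE | SD | Printed |
|---|---|---|---|---|
| Spot CV | (72.96 - 38.06)/2 = 17.45 | 8.34 | 37.29 | 37.29 |
| 24-hour CV | (64.75 - 40.47)/2 = 12.14 | 5.80 | 25.94 | 25.93 |
| Difference | (12.87 + 7.07)/2 = 9.97 | 4.76 | 21.30 | 4.76 |

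The first two rows reproduce as standard deviations. The third reproduces only as a standard error. Taken as an SD, 4.76 would give 2.9 ± 2.093 × 4.76/4.472 = 0.67 to 5.13. Taken as an SE, it gives 2.9 ± 2.093 × 4.76 = -7.06 to 12.86, which matches the printed limits to rounding.

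**2. Two independent checks.**

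- Range: with n = 20 and SD 4.76, no value can lie further from the mean than (19/4.472) × 4.76 = 20.2. The printed extremes lie 50.0 - 2.9 = 47.1 and 2.9 + 43.1 = 46.0 away. With the other 18 values equal, the smallest possible SD is 15.1.
- Correlation: √(37.29² + 25.93² - 2 × 0.83 × 37.29 × 25.93) = 21.4.

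**3. What the correct SD shows.** Approximate 95% limits for one patient's CV difference are 2.9 ± 1.96 × 21.3, or about -39 to +45 points. The row already prints -43.1 to 50.0. The mean comparison is untouched: 2.9/4.76 = 0.61, p about 0.55. This shows no difference in mean CV, but it does not establish equivalence, since no margin is set and the upper limit is 12.9 points.

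**4. Table 2.** Ratios of spot to 24-hour standard error over the six visits are 1.31, 1.36, 1.52, 1.46, 2.20 and 0.80, so similar is generous. Mean reductions, spot minus 24-hour, differ by 2.1, -4.0, -2.3, -10.8, -7.0 and 6.9 points. The sign changes, and N is only 11 to 15. Over Months 3 to 6 (Days 85, 113, 141, 169) the unweighted averages are:

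- 24-hour: (63.2 + 70.8 + 70.9 + 63.3)/4 = 67.05%
- spot: (60.9 + 60.0 + 63.9 + 70.2)/4 = 63.75%

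The gap is 3.3 points, with the spot ratio showing the smaller reduction.

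**5. The correlations.** Fisher's z for r = 0.86 and 156 independent pairs gives 0.813 to 0.896. The printed 0.82 to 0.90 is reached if the unrounded r is near 0.865. The SAP states no method, so this is inference. On percent change, √0.656 = 0.81. The 0.86 is not that figure, because 0.86² = 0.74. It therefore most likely describes levels, as the sentence that reports it suggests. With all 20 patients, √0.774 = 0.88.

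**6. Where the appendix is used.** Sample size rests on feasibility (Protocol Section 7.1, SAP Section 5.1). The primary model in SAP Section 7.1 takes visit, baseline ratio and patient, with no input from Section 10.3. The 24-hour analyses in Section 7.1.2 use data as observed. The correlation within this trial is optional there, and SAP Section 8 notes that few patients have 24-hour data.

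**The case for a change.** The best case for acting is that 24-hour collection is the protocol's preferred method, the primary outcome is something else, and few children here will supply both. Section 10.3 is then most of what a reader has on the link between them. The misprint understates the spread 21.3/4.76 = 4.5-fold, and the closing sentence reads as a claim about individual agreement. The SDs of the two CVs, also called similar, are 37.29 and 25.93; a Pitman-Morgan test at r = 0.83 gives p about 0.011.

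Some of this stands. The cell is wrong, the sentence claims more than the row supports, and the return from 16 to 20 patients should have been explained, because Table 3 concerns the very spot values that were in doubt.

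Much of it carries less weight than it first seems:

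- The text never cites 4.76. It relies on the mean difference, its interval and the correlation, none of which is shown to be wrong.
- The sentence just before the conclusion speaks of similar variability, so minimal can be read as referring to averages.
- The possible narrowness of the interval for r = 0.86 depends on a method the SAP does not state. The percent-change fit is already given under Figure 3.
- The 10.8-point gap is the largest of six visits.
- The SAP does not say whether each CV pools baseline and on-treatment samples, so Table 3 is a weak guide to measurement precision even with the right SD.

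**Conclusion.** The misprint is certain: 4.76 is a standard error, and the SD of the CV difference is about 21.3. The closing sentence should be read as saying that no difference in mean CV was shown, with individual differences from -43.1 to 50.0 points. Both are editorial matters in a background appendix about another study, in older patients, and the row itself lets a reader recover the right value.

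No change to the plan follows. The spot ratio is primary because 24-hour collection is not feasible in every infant and young child, a reason that does not depend on Table 3. The estimate, its confidence interval, the analysis sets and the sample size would be the same whichever number the cell held. If the optional correlation in SAP Section 7.1.2 is run with repeated pairs per child, an analyst would ordinarily allow for clustering or report it descriptively. Re-analysing the earlier study would alter nothing planned here.

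This rests on the printed 95% limits being t-based with 19 degrees of freedom, which the other two rows confirm, and on Section 10.3 having no use beyond the reference in Section 7.1. What remains open is why Table 3 and Figure 2 include the four excluded patients. Their effect on Table 3 cannot be judged from the SAP. On levels, r is 0.86 with 16 patients and 0.88 with 20.
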